5 INTERIM ANALYSIS

No interim analysis is planned.

7 APPENDIX

Partial Date Convention

The detail imputation for partial start dates of AEs as below:

- Partial AE start dates where only the year is known:
 - If year is different from the year of dose date, assume January 1:
 - If year is same as the year of dose date:
 - Assume (dose date + 1 day) if AE started ≤ 7 days after dosing
 - Assume (dose date + 7 days) if AE started 8 to 14 days after dosing
 - Assume (dose date + 14 days) if AE started > 14 days after dosing
 - Assume (dose date + 1 day) if range of days started after dosing was not selected
- Partial AE start dates where only the month and year are known:
 - If year and/or month are different from the year and/or month of dose date, assume first day of the month
 - If year and month are the same as the year and month of dose date:
 - Assume (dose date + 1 day) if AE started ≤ 7 days after dosing

- Assume (dose date + 7 days) if AE started 8 to 14 days after dosing
 - Assume (dose date + 14 days) if AE started > 14 days after dosing
 - Assume (dose date + 1 day) if range of days started after dosing was not selected
- If AE stop date is partially missing, assume December 31 if only the year is known; assume end of the month if only the year and the month are known.

If AE onset date is completely missing, then it will be counted as treatment-emergent AE (TEAE).

Imputed dates will NOT be presented in the listings.

SIGNATURE PAGE

This is a representation of an electronic record that was signed electronically and this page is the manifestation of the electronic signature

Document Name: d5290c00007-sap-ed-2		
Document Title:	Statistical Analysis Plan Edition 2	
Document ID:	CCI [REDACTED]	
Version Label:	2.0 CURRENT LATEST APPROVED	
Server Date (dd-MMM-yyyy HH:mm 'UTC'Z)	Signed by	Meaning of Signature
22-Dec-2021 08:37 UTC	PPD [REDACTED]	Qualified Person Approval
22-Dec-2021 01:35 UTC	PPD [REDACTED]	Content Approval

CCI [REDACTED]

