4.2.2 Secondary Endpoint

4.2.2.1 Definition

4.2.2.1.1 Adverse events

Adverse Events

The term AE is used to include both serious and nonserious AEs and can include a deterioration of a pre-existing medical occurrence. AEs will be collected from the time of signature of informed consent through Day 151.

Treatment-Emergent Adverse Events

A treatment-emergent adverse event (TEAE) will be defined as an AE with the start date on or after the administration date, and up to Day 151.

Serious Adverse Events

AEs and SAEs will be collected from the time of signature of informed consent through Day 151.

Treatment-Emergent Serious Adverse Events

A treatment-emergent serious adverse event (TESAE) will be defined as a SAE with the start date and time on or after the administration date and time, and up to Day 151.

Adverse Events of Special Interest

The occurrence of AESIs defined as AEs of anaphylaxis and other serious hypersensitivity reactions, including immune complex disease (eg, vasculitis, endocarditis, neuritis, glomerulonephritis), or thrombocytopenia following investigational product administration. The SMQ broad and narrow for anaphylaxis, SMQ narrow for hypersensitivity and PT for thrombocytopenia and immune complex disease will be used to extract AESI terms.

New Onset Chronic Disease

An NOCD is a newly diagnosed medical condition that is of a chronic, ongoing nature. It is observed after receiving the investigational product and is assessed by the Investigator as medically significant. Examples of NOCDs include, but are not limited to diabetes, autoimmune disease (eg, lupus, rheumatoid arthritis), and neurological disease (eg, epilepsy). Events that would not be considered as NOCDs are mild eczema, diagnosis of a congenital anomaly present at study entry, or acute illness (eg, upper respiratory infection, otitis media, bronchitis).

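### The SAP's partial-date rule for AE onset ignores the stop date, so an AE known to have ended before dosing can be counted as treatment-emergent (minor)

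*SAP*

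**What the plan says.** SAP Section 4.2.2.1.1 starts AE collection before dosing: "AEs will be collected from the time of signature of informed consent through Day 151". Section 4.2.2.1.3 places the screening visit between Day -28 and Day -2, so some weeks can pass between consent and the injection. The same Section 4.2.2.1.1 defines a TEAE as "an AE with the start date on or after the administration date, and up to Day 151". Section 4.2.2.4 says that AEs occurring before treatment are listed but left out of the summary tables. Its exception is an event that becomes more severe after dosing.

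The Partial Date Convention in Section 7 supplies the onset date when it is incomplete:

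- Month and year known, and different from those of the dose: "If year and/or month are different from the year and/or month of dose date, assume first day of the month".
- Month and year known, under the condition "If year and month are the same as the year and month of dose date": dose date +1, +7 or +14 days according to the post-dose range recorded, and otherwise "Assume (dose date + 1 day) if range of days started after dosing was not selected".
- Only the year known, under the condition "If year is same as the year of dose date": the same four outcomes.
- Onset wholly unknown: "If AE onset date is completely missing, then it will be counted as treatment-emergent AE (TEAE)".

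The stop date has its own line, which only completes a partial stop date to the latest possible day. For example: "If AE stop date is partially missing, assume December 31 if only the year is known".

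**The concern.** All three ranges in the convention are worded as days after dosing. An AE that began before dosing fits none of them, so if its partial start shares the dose month (or the dose year, when the month is also unknown) it drops to the fallback and is given an onset on the day after dosing. This happens even when the recorded stop date is earlier than the dose date. A wholly missing onset is treated in the same way, without any check.

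An event with a pre-dose stop date cannot have started on or after administration. Nor can it have worsened after dosing. By the SAP's own definitions it is pre-treatment, yet the Appendix sends it to the TEAE summaries. Safety is a secondary objective and is reported only by counts and percentages in two small groups, so a wrongly flagged event changes the reported result directly.

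**Working it through.** The plan gives no figure to reproduce. The check is to apply the convention as written to example dates and compare the result with the SAP's TEAE definition.

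**Inputs.** From SAP Section 7: the branches above. From Section 4.2.2.1.1: a TEAE has an onset on or after the dose date. From Section 1.2: 18 nirsevimab and 6 placebo subjects planned. Assumed for illustration: dose date 20 March 2021 and no post-dose range recorded.

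**Rule.** If the partial start shares the dose month and year (or, with only a year, the dose year), imputed onset = dose date + 1 = 21 March 2021. If it differs, imputed onset = first day of the stated month, or 1 January of the stated year.

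| Recorded start | Recorded stop | Onset under the rule | Class under the rule | Class with a stop-date check |
|---|---|---|---|---|
| March 2021 | 14 March 2021 | 21 March 2021 | TEAE | pre-treatment |
| 2021 | 1 March 2021 | 21 March 2021 | TEAE | pre-treatment |
| wholly missing | 14 March 2021 | none needed | TEAE | pre-treatment |
| February 2021 | 1 March 2021 | 1 February 2021 | pre-treatment | pre-treatment |
| 2020 | 1 March 2021 | 1 January 2020 | pre-treatment | pre-treatment |

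In the first row the imputed onset is 21 - 14 = 7 days after the event ended. The first three rows are wrong under the SAP's own definition. The last two show the limit of the problem: a known earlier month, or a known earlier year, stays pre-treatment.

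**Partial stop dates.** Completing a partial stop date to its latest possible day keeps the check cautious. A start of 2021 with a stop of February 2021 completes to 28 February, before the dose, so the event is pre-treatment. A start and stop both recorded only as March 2021 complete to a stop of 31 March, which is not before the dose, so the existing rule and its TEAE flag stand.

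**Size per subject.** One wrongly flagged subject adds at most 1/18 = 5.6 percentage points in the nirsevimab group or 1/6 = 16.7 points in the placebo group.

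**The case against.** Several points on the other side are sound.

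- **Defaulting to treatment-emergent is the ordinary cautious choice when timing is unknown.** This stands. Where the stop date is missing, ongoing, or on or after dosing, the existing rule can remain. The error is confined to cases in which the stop date settles the question.
- **The CRF is not shown and may hold a pre-dose option.** It may, but the SAP convention does not use one. A programmer might also fall back on Section 4.2.2.4, but the Appendix does not refer to it.
- **A reader might infer that the outputs will show negative durations.** The documents do not support this. Section 3.3.1.1 leaves durations partial or missing in the listings when the event date is incomplete, and Section 7 keeps imputed dates out of the listings. The consequence is the TEAE flag.
- **A reader might infer that a large share of pre-dose AEs with partial dates is misclassified.** If onset were uniform over the 28 days before dosing and dosing were spread evenly over 2021, 52% would share the dose month and 96% the dose year. Neither assumption is in the SAP, and the month share runs from 0 to 28 of the 28 days depending on the dose day. More importantly, these shares show how often the branch could be entered whatever the stop date. They do not measure the events that a stop-date check would correct.
- **The percentage-point figures are upper limits.** Subjects are counted once per SOC or PT, so the any-TEAE row moves only if the subject has no other TEAE.
- **The impact is small.** The error needs a pre-dose AE, an incomplete or missing onset and a stop date before dosing, all in one event. It over-counts TEAEs and hides none, it can occur in either group, and the AE listing carries the recorded stop date. The PK primary endpoint is untouched.

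These points limit the frequency and size of the error. They do not make the classification right when it occurs.

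**Conclusion.** The rule is wrong as written, and the matter is minor. An AE whose recorded or latest possible stop date is before dosing is still counted as a TEAE in three situations: its start has only month and year, matching those of the dose; its start has only a year, matching the dose year; or its start is wholly missing. The first two assume that no post-dose range was recorded, as should be so for a pre-dose event. In each, the Appendix contradicts Sections 4.2.2.1.1 and 4.2.2.4.

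The effect is at most 5.6 points per nirsevimab subject and 16.7 points per placebo subject, at the planned group sizes. The number of such cases cannot be derived from the SAP. With 24 healthy adults at one centre, few are to be expected.

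**What to change.** Add a first step to the Partial Date Convention in SAP Section 7, ahead of the start-date rules:

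- If the AE stop date is before the dose date, classify the AE as pre-treatment and do not impute an onset later than the stop date. A partial stop date is first completed to its latest possible day, as the Appendix already does.
- Otherwise apply the existing start-date rules unchanged.
- Apply the same check to AEs with a wholly missing onset before counting them as TEAEs.

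The cost is about two sentences in the Appendix and a few lines of derivation code. It needs no new data and leaves the cautious default in place wherever the timing is truly unknown.
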